7.4 Common Calculations

For quantitative measurements, change from baseline will be calculated as:

(Test Value at Visit X – Baseline Value).

The effect size will be calculated as:

[(Test Value at Visit X – Baseline Value)/ Baseline SD].

7.5 Software Version

All analyses will be conducted using Statistical Analysis System (SAS) version 9.4 or higher.

8. STATISTICAL CONSIDERATIONS

8.1 Statistical Tests and Confidence Intervals

Unless otherwise specified in the description of the analyses, a two-sided 95% CI will be considered as a default (alpha= 5%). The equivalence margin is set to 2/7 wet nights with an expected proportion of 0.95 and 0.80 wet nights, respectively for continuing and discontinuing use of absorbent pants group.

No confirmatory testing is planned, p-values are provided as descriptive representations of the data.

Document:	Y:\Kimberly-Clark\DryNites\Documentation\SAP\DryNites_SAP_v1.0_20200203			
Author:	[name] Version Number:		1.0	
		Version Date:		03Feb2020
Template No.: RWI_TP_BIOS0013 Revision 1			Reference:	RWI_WI_BIOS0015
Effective Date: 15Jun2018				

Statistical Analysis Plan

8.2 Adjustments for Covariates and Factors to be Included in Analyses

The baseline of any applicable Patient Reported Outcomes (PRO) will be used as covariate in the analysis of covariance (ANCOVA) planned on secondary endpoints analysis.

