# 4.3.5. Methods for Assigning Patients to Treatment Groups

A patient randomisation list will be produced using permuted block randomisation stratified by age group (4–<6 years old and  $\ge6-8$  years old) and a 2:1 group allocation for discontinuation or continuation of the use of DryNites® pyjama pants.

When a patient is qualified for entry into the randomised treatment period, treatment assignment will be performed by means of an IWRS on a central level on Visit 2 (Day  $28 \pm 7$  days).

Before the study is initiated, the log in information and directions for the IWRS will be provided to each study centre.

The Investigator or his/her delegate (study coordinator) will log on to the EDC and confirm that the patient fulfils the eligibility criteria and proceed with the randomisation. Participants will be assigned a unique number (randomisation number) in ascending numerical order on the next available record in the group at each study centre. The randomisation number encodes the participant's assignment to 1 of the 2 arms of the study (No Pants arm or DryNites® arm).

The treatment assignment (Discontinuation vs. continuation of DryNites®) will be captured in the EDC from the IWRS.

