15.1 Primary Analysis

The primary analysis will be performed separately for age groups for the PAS comparing the 95% CI for the difference between the means of average wet nights at the end of intervention period for the 2 groups with the predefined margin. Being the primary analysis focused on last week of the intervention period (lasting from randomisation to Visit 3) and the equivalence margin reported as 2/7 (two nights over a week), the average number of wet nights was chosen as reliable outcome on primary endpoint.

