15.1.3 Primary Analysis of Primary Variable

The primary objective of this study is to demonstrate if discontinuation of nocturnal use of absorbent pants in children with NE has any impact on the rate of spontaneous resolution of NE, compared with continued use of absorbent pants, over a period of 4 weeks.

The primary effectiveness analysis will be performed for the PAS comparing the 95% CI for the difference between the means of average wet nights at the end of intervention period for the 2 groups with the predefined margin ($\delta = 2/7$). If the CI lies strictly within [- δ , + δ], the study hypothesis will be demonstrated. Difference in means and CI will be generated by PROC TTEST for independent groups.

Primary analysis will be also repeated by age groups (4–<6 years and \geq 6–8 years).

Document:	Y:\Kimberly-Clark\DryNites\Documentation\SAP\DryNites_SAP_v1.0_20200203		
Author:	[name]	Version Number:	1.0
		Version Date:	03Feb2020
Template No.: F	RWI_TP_BIOS0013 Revision 1		Reference: RWI_WI_BIOS0015
Effective Date:	15Jun2018		

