15.2.3 Analysis of Secondary Variables

15.2.3.1 Analysis of Secondary Variables

Analyses of PinQ, WHOQoL-BREF, PDSS and CIS questionnaires will be provided by group on the Randomised Set.

Frequency distribution and descriptive statistics, when applicable, will be provided by visit for each item of questionnaires, while summary statistics for total scores, domain scores and changes from baseline will be provided as applicable.

The effect size will be also presented as descriptive statistics of ratio between the change from baseline and baseline SD.

Document:	Y:\Kimberly-Clark\DryNites\Documentation\SAP\DryNites_SAP_v1.0_20200203		
Author:	[name]	Version Number:	1.0
		Version Date:	03Feb2020
Template No.: F	RWI_TP_BIOS0013 Revision 1		Reference: RWI_WI_BIOS0015
Effective Date:	15Jun2018		

The percentage of patients with change from baseline ≥ 0.5 time the baseline SD will be also provided.

For applicable questionnaires an ANCOVA with baseline PROs value as covariate will be performed. Group comparisons will be performed for the difference in least squares means (LSMean) at Visit 3. The LSMean (standard error [SE]) by group and visit (if applicable), the LSMean difference between groups, along with 95% confidence limits of the group differences and the p-value for the group comparison will be displayed as purely exploratory. For the change from baseline, p-value for the within-group difference will also be displayed as purely exploratory. The Absorbent Pants Clinical Trial Questionnaire administered at study entry, and the DryNites® Clinical Trial Questionnaire administered at the end of the run-in period, will be analysed descriptively for the Screened Set.

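### Age group stratifies the randomisation but is left out of the pooled primary comparison and the PRO ANCOVA; adding it is a free improvement whose benefit depends on age being prognostic

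*SAP*

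**What the plan says.** **Design.** Protocol 4.3.5 specifies "permuted block randomisation stratified by age group" with "a 2:1 group allocation for discontinuation or continuation of the use of DryNites® pyjama pants". The two strata are 4–<6 and ≥6–8 years, intended to be of similar size (Protocol 4.1).

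**Pooled primary comparison.** SAP 15.1.3: "Difference in means and CI will be generated by PROC TTEST for independent groups". No covariate is named, nor is the choice between the pooled-variance and Satterthwaite intervals that the procedure offers.

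**Questionnaires.** SAP 8.2 is the section on adjustment factors. It names one: "The baseline of any applicable Patient Reported Outcomes (PRO) will be used as covariate". SAP 15.2.3.1 agrees: "For applicable questionnaires an ANCOVA with baseline PROs value as covariate will be performed". Protocol 5.4.2 says the same. SAP 15.3 sets out the covariance structure and degrees of freedom of the repeated-measures model but does not list its fixed effects.

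**Where age does appear.** It defines the subgroup analyses (SAP 8.4) and enters the imputation model for the primary outcome (SAP 15.1.2). SAP 15.1 states: "The primary analysis will be performed separately for age groups for the PAS". SAP 15.1.3 instead describes a pooled analysis first and then adds: "Primary analysis will be also repeated by age groups". Protocol 5.4.2 applies the margin to a single two-group comparison, while Protocol 5.2 sizes each age group on its own.

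**The concern.** Stratified randomisation balances the arms on age, so a difference between age groups contributes almost nothing to the true sampling error of the treatment difference. An unadjusted two-sample interval still counts that difference as residual noise. If younger and older children differ in wet nights at Week 4, the interval is wider than the design requires, and in an equivalence trial a wider interval makes success harder.

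Two features add to the case:

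- Balance holds in the randomised set, but the Primary Analysis Set drops major violators and analyses use non-missing values (SAP 6.4, 8.3). If losses differ by age and arm, some balance goes; a stratum term protects against that.
- For PinQ and PDSS the stratum decides the respondent: the child in the older group, the parent or carer in the younger (Protocol 4.5.2.1, 4.5.2.3). A level difference between strata is therefore plausible on those scales.

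**Working it through.** **1. The plan's own figure.** Protocol 5.2 states 99% power with 15 continuing children (45 in all), 7 nights each, wet-night probabilities 0.95 and 0.80, margin 2/7 and a 95% interval. Simulating 40,000 data sets at 15 v 30 on the proportion scale gives 97.7% with a night-level Wald interval, 97.1% with a Welch interval on each child's proportion and 91.2% with the pooled-variance t interval. The first two are within 2 points of the stated figure.

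**2. Inputs for the adjustment.** Two equal strata, 2:1 allocation, 30 v 60 children (2 × 45 = 90), arm means 0.95 and 0.80. The age gaps are assumptions: g0 in the continuation arm and g1 in the discontinuation arm, placed symmetrically about the arm mean.

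**3. Formula (pooled variance).**

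- Within-stratum variance per child: [p(1−p) − g²/4]/7, multiplied by 1 + 6ρ if a child's nights have correlation ρ.
- Total variance: the within-stratum variance plus g²/4, averaged over arms with weights 1/3 and 2/3.
- Part removed by a stratum term: d²/4, with d = (g0 + 2·g1)/3.
- Width ratio, adjusted to unadjusted: √(1 − (d²/4)/total).

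Worked case, g0 = 0.05, g1 = 0.10, ρ = 0:

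- Within: (0.0475 − 0.000625)/7 = 0.006696 and (0.16 − 0.0025)/7 = 0.0225.
- Total: [(0.006696 + 0.000625) + 2(0.0225 + 0.0025)]/3 = 0.019107.
- d = 0.25/3 = 0.0833, so d²/4 = 0.001736.
- Ratio: √(1 − 0.001736/0.019107) = 0.953.

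**4. Simulated ratios** (20,000 data sets per case, pooled-variance t against treatment plus stratum, N = 90):

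| Gap, continue/discontinue | ρ = 0 | ρ = 0.3 (assumed) |
|---|---|---|
| none | 1.000 | 1.000 |
| 0.02/0.05 | 0.989 | 0.996 |
| 0.05/0.10 | 0.953 | 0.982 |
| 0.08/0.20 | 0.852 | 0.937 |
| 0.09/0.30 | 0.755 | 0.878 |

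The formula gives 0.989, 0.953, 0.854 and 0.757 for the four non-zero rows at ρ = 0. Ratios at N = 120 are essentially the same.

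**5. Effect on the decision (gap 0.05/0.10, N = 90).** Power is 99.8% unadjusted and 99.9% adjusted at ρ = 0. At ρ = 0.3, which departs from the plan's assumptions, it is 79.1% and 80.2%. Coverage at ρ = 0 is 98.7% unadjusted and 98.2% adjusted, so the omission errs on the cautious side.

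**6. Why coverage exceeds 95% even after adjustment.** These intervals use one common variance, while the larger arm has the larger variance. With no age effect the variances are 0.0475/7 = 0.006786 and 0.16/7 = 0.022857.

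- Common-variance standard error: √{[(29 × 0.006786 + 59 × 0.022857)/88] × (1/30 + 1/60)} = 0.0296.
- Arm-specific standard error: √(0.006786/30 + 0.022857/60) = 0.0246.

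The first is 20% larger, so the unstated variance choice matters more than the stratum does on modest gaps.

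**7. Does the gain survive arm-specific variances?** For the 0.05/0.10 case, the unadjusted variance of the difference is 0.007321/30 + 0.025/60 = 0.000661. Removing the common gap of 0.0833 leaves [0.006696 + (0.05 − 0.0833)²/4]/30 + [0.0225 + (0.10 − 0.0833)²/4]/60 = 0.000609. The ratio is √(0.000609/0.000661) = 0.960, a similar gain of about 4%.

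Width ratios do not depend on whether the outcome is a proportion or a count of nights. The power figures take 2/7 as a proportion, as the Protocol 5.2 simulation does.

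**The case against.** The strongest reply is that the gain rests on an age effect the documents never quantify, in a population chosen to be homogeneous: at most one dry night a month on average, then seven wet nights out of seven before randomisation (Protocol 4.3.1, 4.7.3). Protocol 5.4.6 even allows that neither arm may change. This stands; with no age effect the ratio is 1.000.

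It is also true that analyses within age group already condition on the stratum. If SAP 15.1 governs and the separate analyses are primary, the point does not touch the primary result. It applies where the pooled comparison is used, which is how Protocol 5.4.2 and SAP 15.1.3 read.

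For the questionnaires, WHOQoL-BREF and CIS are completed by the parent or carer in both strata, so the respondent argument is confined to PinQ and PDSS. Even there the ANCOVA adjusts for a baseline score from the same type of respondent, which may absorb much of the difference. The SAP calls these comparisons purely exploratory (15.2.3.1).

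A reader might infer that the planned intervals are certainly too wide, perhaps by 20%. The 20% comes from √(0.15² + 0.20²/4)/0.15 = 1.20, with one gap of 0.20 in everyone. In a continuation arm averaging 0.95 with equal strata, that gap would need stratum values of 0.85 and 1.05, which is impossible; the largest possible gap there is 0.10. Arm-specific gaps can still produce large ratios, as the last two table rows show, but they need discontinuation gaps of 0.20 or more, and nothing in the documents points to these.

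**Conclusion.** The omission is documented and worth correcting as a free improvement. If age is prognostic, the unadjusted pooled interval is conservative. Adjustment would narrow it by about 1–5% on assumed gaps of 0.02/0.05 to 0.05/0.10, or by 0.4–2% if nights within a child correlate at 0.3. If age is not prognostic, nothing is gained and essentially nothing lost. Equivalence power under the plan's assumptions is almost unchanged.

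The documents do not support reading this as a flaw in validity: omitting the stratum does not make equivalence easier to claim. Nor do they show that age is strongly related to the questionnaire scores. That link is plausible for PinQ and PDSS, but its size cannot be computed because no standard deviations or correlations are given.

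**What to change.** - **SAP 15.1.3:** replace the t-test for the pooled comparison with a linear model of the Week-4 outcome on treatment and age stratum, allowing a separate residual variance in each arm. Report the adjusted difference and its 95% interval. This also settles the unstated choice between pooled and Satterthwaite intervals.
- **SAP 8.2 and 15.2.3.1:** add age stratum to the ANCOVA alongside the baseline score.
- **SAP 15.3:** list the fixed effects of the repeated-measures model and include age stratum.
- **SAP 15.1 and 15.1.3:** state whether the pooled or the separate age-group analysis is primary, consistently with Protocol 5.2 and 5.4.2.

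If the sponsor prefers to leave the stratum out, one sentence of justification in SAP 8.2 would do. The cost is SAP wording and minor programming, with no new data: age group is already recorded for randomisation.

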8.3 Missing Data

Should missing data occur, the data will be analysed as recorded in the electronic CRF (eCRF), that is, analyses will be performed on patients with non-missing values. However, the amount of missing values for data elements will be reported, and the likely impact of missing data on the analysis and the pattern of the missing information will be assessed.

Depending upon the amount of missing data, and whether there is evidence of bias in the missing data (e.g., differences between patients with and without missing data), multiple imputation (detailed in Section 15.1.2), may be performed and a sensitivity analysis will be carried out comparing the results from the complete case analysis (where records with missing data will be dropped) and the full set analysis including the imputed data.

Missing safety data will not be imputed. Partial date handling is described in Appendix 2.

8.4 Examination of Subgroups

Subgroup analyses will be conducted considering the age group stratification factor at randomisation.

9. OUTPUT PRESENTATIONS

Appendix 1 shows conventions for presentation of data in outputs.

The templates provided with this SAP describe the presentations for this study and therefore the format and content of the summary TLFs to be provided by IQVIA RWES Biostatistics.

Document:	Y:\Kimberly-Clark\DryNites\Documentation\SAP\DryNites_SAP_v1.0_20200203		
Author:	[name]	Version Number:	1.0
		Version Date:	03Feb2020
Template No.:	RWI_TP_BIOS0013 Revision 1	I	Reference: RWI_WI_BIOS0015
Effective Date:	15Jun2018		

Statistical Analysis Plan

10. DISPOSITION AND WITHDRAWALS

The total number of patients included in each analysis set described in Section 6 along with the number of patients for each of following categories will be provided as disposition analysis:

- Patients consented, overall and by age group (4–<6 years and \geq 6–8 years)
- Patients randomised, overall and by age group (4–<6 years and \geq 6–8 years)
- Patients who completed the 4-week intervention period, overall and by age group (4-<6 years and ≥6-8 years)
- Patients who entered the extension period, overall and by age group (4–<6 years and ≥6–8 years)
- Patients who completed the extension period, overall and by age group (4-<6 years and ≥6-8 years)
- Time and reasons for discontinuation of the study, overall and by age group (4–<6 years and \geq 6–8 years).

For all categories except the Screened Set, the percentages will be calculated using the number of randomised patients as the denominator for each treatment group.

11. DEMOGRAPHIC AND OTHER BASELINE CHARACTERISTICS

Demographic data and other baseline characteristics, including characteristics of NE (as collected on eCRF), will be presented for the SCR and RND set.

No statistical testing will be carried out for demographic or other baseline characteristics.

The following demographic and other baseline characteristics will be reported for this study:

- Age (years) calculated relative to date of consent
- Sex

Document:	Y:\Kimberly-Clark\DryNites\Documentation\SAP\DryNites_SAP_v1.0_20200203		
Author:	[name] Version Number:		1.0
		Version Date:	03Feb2020
Template No.: I	RWI_TP_BIOS0013 Revision 1		Reference: RWI_WI_BIOS0015

Effective Date: 15Jun2018

- Race
- Ethnicity
- Weight (kg)
- Height (cm)
- Body mass index (BMI) (kg/m²)
- BMI as category

11.1 Derivations

- Age (years) will be derived in using Month and Year of Birth, and calculated relative to ICF signature, as follows:
 - Age (years) = (ICF Signature year Birth year) if ICF Month \geq Birth Month,
 - \circ Age (years) = (ICF Signature year Birth year 1) if ICF Month < Birth Month.
- Calculated age will be classified as per randomisation stratum as:
 - \circ 4–<6 years;
 - $\circ \geq 6-8$ years;

Edit checks were included in the EDC to avoid wrong stratum selection but in case of difference between the calculated stratum and the one used at randomisation, the violation might be considered as reason for exclusion from the PAS.

- Time to discontinuation in weeks = (End of study date ICF date + 1)/30.5;
- Weight (kg) = weight (pounds)*0.453592;
- Height (cm) = height (inches)*2.54;
- BMI $(kg/m^2) = weight (kg)/height (m)^2;$

Document:	Y:\Kimberly-Clark\DryNites\Documentation\SAP\DryNites_SAP_v1.0_20200203		
Author:	[name]	Version Number:	1.0
		Version Date:	03Feb2020
Template No.:	RWI_TP_BIOS0013 Revision 1	Reference:	RWI_WI_BIOS0015

Effective Date: 15Jun2018

- Calculated BMI will be classified as follows based on comparison with country specific reference data:
 - Underweight (<5th percentile for sex and age),
 - Normal (from 5th to less than 85th percentile for sex and age),
 - Overweight (from 85th to less than the 95th percentile for sex and age),
 - Obese (\geq 95th percentile for sex and age).

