Study specific mandated clinic visits will be required as part of the participation in this study. Baseline, randomisation, and any subsequent visit (i.e., Visit 3 and 4) can also be performed remotely in case the patient cannot visit the site in person. Participants will be assessed on Day 0 (baseline), Day  $28 \pm 7$ days (end of run-in and randomisation), Day  $56 \pm 7$ days (end of intervention/core trial period), and Day  $84 \pm 7$ days (end of extension period).

Participants will be reimbursed for their travel expenses, where applicable.

[figure not shown]
Dry and wet nights will be captured every day from the start of the run-in period to discontinuation of the study through an electronic diary, accessible through the parent's/carer's own device (smart phone, tablet, or computer).

Quality of life (QoL) and sleep questionnaires will be completed by children and parents/carers in electronic format on-site during the clinic visit, using site-based hand-held devices (e.g., tablets) or computers, from randomisation onwards. In case the questionnaires are not completed during the clinic visit or if a visit is performed remotely, the questionnaires will be accessible through the parent's/carer's own device. Questionnaires will be accessible after the visit and should be completed as close to the visit as possible (and before the next visit).

The perception of the absorbent products will be assessed by 2 questionnaires, at study entry (on previous absorbent products) and at the end of the run-in period (on DryNites®, compared to the previously used absorbent pants/nappies).

An overview of the trial design is provided in Figure 1.

Figure 1 Study Design

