4. STUDY DESIGN

4.1 General Description

This is an 8-week randomised, open-label, 2-arm, parallel-group Phase IV trial with a 2:1 allocation ratio for discontinuation of continuation of use of DryNites® absorbent pants in children with NE, with an optional 4-week extension period.

Eligible patients will be children with monosymptomatic NE, not previously treated for NE, and managed with absorbent pants/nappies (any brand) for a minimum of 6 months. Participants must be dry at day for at least 6 months. Participants will be divided in 2 age groups of similar size. The younger age group will be comprised of participants aged 4–<6 years old and the older age group will be comprised of participants aged \geq 6–8 years old.

One hundred and twenty participants should be recruited, balanced between the 2 age groups. The equivalence margin is set to 2/7 wet nights with an expected proportion of 0.95 and 0.80 wet nights, respectively for continuing and discontinuing use of absorbent pants group. The power is set to 99%.

The study consists of 3 consecutive periods of 4 weeks each, including the run-in, the intervention (core trial) period, and the extension period.

Participant meeting the eligibility criteria will enter 4-week run-in period, when all participants will be assigned to using DryNites® every night.

Participant meets the inclusion criterion of NE 7 nights per week during the last week of the run-in period will be randomised to participate in 4-week intervention (core trial) period. Participants will be assigned to either stopping the use of absorbent pants or continuing DryNites® in a 2:1 ratio.

Document:	Y:\Kimberly-Clark\DryNites\Documentation\SAP\DryNites_SAP_v1.0_20200203		
Author:	[name] Version Number:		
		Version Date:	03Feb2020
Template No.: RWI_TP_BIOS0013 Revision 1 Refer		Reference: RWI_WI_BIOS0015	

Effective Date: 15Jun2018

Following completion of the 4-week intervention period, participants will be invited to participate in the optional 4-week extension when participants will remain on their randomly assigned treatment for an additional 4 weeks.

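### SAP 11.1 labels time to discontinuation in weeks but divides days by 30.5, a days-per-month divisor, so the unit and the formula contradict each other

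*SAP*

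**What the plan says.** SAP section 11.1 (Derivations) defines the variable in one line. It opens with the unit, "Time to discontinuation in weeks = (End of study date", and in full it reads: "Time to discontinuation in weeks = (End of study date ICF date + 1)/30.5". The minus sign between the two dates is missing from the extracted text. The age formula in the same section shows the same gap, so this is treated as a loss in reading the PDF and not as an error in the plan. The stated unit and the divisor are both legible.

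SAP section 10 commits to reporting the variable in the disposition analysis: "Time and reasons for discontinuation of the study, overall and by age group". Protocol section 5.4.2 lists the same output but gives neither a formula nor a unit. SAP section 4.3, which records changes from the protocol, does not mention it.

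The trial is laid out in weeks. SAP section 4.1 says: "The study consists of 3 consecutive periods of 4 weeks each, including the run-in, the intervention (core trial) period, and the extension period". Protocol section 4.1 places the later visits at Days 28, 56 and 84, each with a window of 7 days either side.

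**The concern.** The numerator is a number of days. Dividing days by 30.5 gives months, so the line cannot be right as it stands: either the divisor or the label is wrong. A programmer who follows the SAP literally will produce a table headed in weeks that contains months.

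At stake is whether the reported timing of discontinuation can be read correctly. In a trial built from 4-week blocks, a reader will naturally compare the times with week 4 (end of run-in) and week 8 (end of intervention). Under the formula, exits at either point would be shown at under 2 weeks.

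**Working it through.** **Inputs**

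- Formula, unit and divisor: SAP section 11.1.
- Exit days used as examples: 28, 56 and 84, the nominal visit days in Protocol section 4.1. Day 91 is the last day of the final visit window (84 + 7).
- Assumption: consent is signed on Day 0, as the schedule of assessments (Protocol Table 2) places it at Visit 1. Earlier consent would lengthen the day counts but leave the ratio unchanged.

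The SAP gives a rule and no worked value, so there is no stated figure to reproduce. The check is of units.

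**Step 1: what the divisor represents.** An average month is 365.25/12 = 30.44 days. A week is 7 days. The figure 30.5 is therefore a days-per-month divisor.

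**Step 2: the SAP formula against weeks.** Counted days = exit day − consent day + 1.

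| Exit day | Counted days | SAP formula (÷ 30.5) | Weeks (÷ 7) |
|---|---|---|---|
| 28 | 29 | 0.95 | 4.14 |
| 56 | 57 | 1.87 | 8.14 |
| 84 | 85 | 2.79 | 12.14 |
| 91 | 92 | 3.02 | 13.14 |

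**Step 3: size of the discrepancy.** The ratio of the last two columns is 30.5/7 = 4.357, or 4.36. It does not depend on the exit day, so it is the same for every participant.

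**Step 4: range of the reported values.** A value of 4 under the SAP formula needs 4 × 30.5 = 122 counted days. The latest scheduled exit gives 92. Even with the extra week of run-in that Protocol section 4.3.4 allows on re-screening, Day 98 gives 99 counted days and 99/30.5 = 3.25. Every scheduled exit, including completion of the extension, would therefore carry a value below 4.

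**Step 5: where the variable is used.**

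- The primary variable is a count of wet nights from the diary over the last 7 days of the intervention period (SAP 15.1.1), compared through a t-test confidence interval (SAP 15.1.3).
- The multiple imputation model (SAP 15.1.2) uses the primary outcome, randomisation group, run-in wet nights, age and sex.
- The secondary ANCOVA (SAP 15.2.3) uses the baseline questionnaire score.
- The definition of treatment-emergent events (SAP 16.1 and Appendix 1) uses event dates.

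None of these uses time to discontinuation.

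**The case against.** The strongest objection is that the direction of the error is not known. If the author meant months, the values are right and one word is wrong. That stands. The documents show a contradiction and do not say which half was intended. The statement that the values are too small holds only with the weeks label kept. Study periods defined in weeks make 7 the more natural divisor, but they do not prove the intent.

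A reader might also infer that the error makes dropout by period unreadable. The documents do not support that. The same disposition analysis (SAP section 10, Protocol section 5.4.2) separately counts children consented, randomised, completing the intervention, entering the extension and completing it, overall and by age group. Losses in each period can be read from those counts without this variable. SAP section 7 also plans individual patient listings on the Screened Set.

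Nor would dividing by 7 give exact timing relative to randomisation. The formula starts from consent, while the SAP's reference start date is randomisation (SAP 7.1). With the visit windows and a possible extra run-in week, weeks from consent match the study periods only approximately. The correction restores the unit and does no more.

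Finally, the error may well be noticed. A child who completes all 12 weeks but is shown at 2.79 weeks, less than the 4-week run-in, looks implausible. That makes a misled reader less likely, but it does not make the written rule correct.

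**Conclusion.** The derivation is internally inconsistent as written. With the weeks label kept, and the formula programmed literally, every value in the time-to-discontinuation summary is too small by a factor of 4.36. That factor rests only on the two numbers 30.5 and 7. The worked examples also assume consent on Day 0.

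This is a minor point. It affects one descriptive summary. It does not touch the equivalence conclusion, the sample size, the questionnaire comparisons, the safety tables or the period-by-period disposition counts.

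**What to change.** In SAP section 11.1, replace 30.5 with 7. This keeps the label and matches the weekly structure of the trial. Alternatively, keep 30.5 and relabel the variable as months, which also removes the contradiction but is less convenient beside periods given in weeks.

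Whichever is chosen, check that the disposition program and table shell carry the same unit and divisor. A table footnote saying that time runs from consent would help the reader.

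The cost is one edited number or word in the SAP and a short programming check. No data collection, analysis set or other planned analysis changes.
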